13.1.4.1 Efficacy Endpoints

Primary efficacy endpoint: The proportion of subjects in each treatment group who experience successful resolution of LI where “success” is defined as clear/almost clear overall and at least a 2-grade change from Baseline at Day 90/EOT in the Double-blind Period on the 5-point IGA scale.

Secondary: The secondary endpoints are as follow:

- The difference in mean scores between the active trifarotene cream HE1 and vehicle groups in the following assessment indices from Baseline through Day 90:
 - 5-point VIIS scale for scaling
 - Individual score for roughness (Scale: 0–4)
 - Palm/sole Assessment (Scale: 0–4)
 - Quality of life per DLQI and cDLQI
- The difference in proportion of subjects with presence of fissures on palm/soles (presence/absence, number of fissures, and pain associated with fissures [on a 0-3 scale]) at Day 90 between the active trifarotene cream HE1 and vehicle groups

Exploratory: The exploratory endpoints are as follow:

- The difference in mean ectropion scores (ESS of 0–8) between the active trifarotene cream HE1 and vehicle groups from Baseline through Day 90
- The difference in quality of life per EQ-5D-5L and EQ-5D-Y scores between the active trifarotene cream HE1 and vehicle groups from Baseline through Day 90

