9.8.1 Permitted Therapies

Subjects will be advised on permitted emollient(s) for use as often as needed on nontreatment days during the study; on treatment days, the use of emollient(s) is permitted except within 4 hours before or after study drug application. Similarly, protective sunscreen should be applied as often as needed, except within 4 hours before or after study drug application. Subjects may use their standard of care treatment on their faces and/or palms/soles after the Week 4 assessment if they experience a worsening of IGA in those areas. In the US/EU, this may include compounded emollients with keratolytics (alpha or beta hydroxyl acids) and/or urea. These standard of care treatments should be approved by the investigator and documented in the eCRF.

Subjects who enter the OLE must stop standard of care treatment. If they experience a worsening of IGA they may use standard of care treatment on their faces and/or palms/soles after the Week 16

visit if the standard of care does not contain prohibited medications. If those standard of care treatments include prohibited medications, the subject should be discontinued from the study.

Other concomitant medications are allowed (e.g., analgesics, antihistamines), but should be limited to those medications considered necessary. All concomitant medications, both prescribed and over-the-counter, should be recorded in the eCRF.

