9.8.2 Prohibited Therapies

The medications listed in [Table 9-1](#) are prohibited during the study. Balneotherapy is also prohibited during the Screening Period and during the study.

Subjects may not use concomitant keratolytics such as urea, salicylic acid, alpha, or beta hydroxyacids. Subjects may not use topical or systemic retinoids. Subjects may not take more than 3500 IU/day Vitamin A (e.g., as in a multivitamin). Use of benzoyl peroxide is permitted on nontreatment days for subjects with concomitant acne only); it must not be applied on treatment days due to risk of inactivation of trifarotene by benzoyl peroxide.

Subjects receiving excluded therapies will be ineligible for study enrollment or for continued treatment in the study, at the investigator's discretion with consultation with Mayne Pharma LLC and the medical monitor. For enrolled subjects who require prescription of a systemic azole, the principal investigator should discuss with the medical monitor whether the subject may continue in the study.

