10.3.1.1 Investigator's Global Assessment

The primary endpoint is the number of subjects in each treatment group who experience successful resolution of LI where “success” is defined as clear/almost clear and at least a 2-grade change from Baseline at Week 12/EOT in the Double-blind Period on a 5-point IGA full body scale.

The investigator will rate the subject's condition using the 5-point IGA at each time point shown in the Schedule of Events (Section 2.2).

The IGA will be measured on a 5-point scale, excluding the following areas: knees, elbows, neck, palms, soles, axillae, groin, and scalp:

0	Clear	No scaling and no roughness
1	Almost Clear	Occasional fine scales; hardly palpable roughness (mostly smooth)
2	Mild	Small and fine scales predominate; no more than a few large scales; mild roughness on palpation
3	Moderate	Some large scales that may be thick; coarse roughness on palpation
4	Severe	Confluent, primarily large (>1 cm), thick scales with plate-like hyperkeratosis

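### Section 9.8.1 allows keratolytics on the face, palms and soles after the Week 4 assessment, Section 9.8.2 forbids the same agents, and the trigger for use cannot be scored on palms and soles

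*Protocol*

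**What the plan says.** The text at issue is Section 9 as it stands under Amendment 2, the latest Section 9 in the document. A later version is shown only from Section 13 onward, so its Section 9 cannot be checked.

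- **Permission, Double-blind Period (9.8.1).** "Subjects may use their standard of care treatment on their faces and/or palms/soles after the Week 4 assessment if they experience a worsening of IGA"; the worsening has to be at those same sites. On the agents, the section adds: "In the US/EU, this may include compounded emollients with keratolytics (alpha or beta hydroxyl acids) and/or urea". There is a control on this: "These standard of care treatments should be approved by the investigator and documented in the eCRF".
- **Prohibition (9.8.2 and Table 9-1).** "Subjects may not use concomitant keratolytics such as urea, salicylic acid, alpha, or beta hydroxyacids". The medications in Table 9-1 "are prohibited during the study. Balneotherapy is also prohibited during the Screening Period and during the study", and that table has a row for topical keratolytics that names urea, lactic acid and salicylic acid. Subjects on excluded therapies may become ineligible for continued treatment, at the investigator's discretion after consultation.
- **Open-label extension (9.8.1, second paragraph).** Standard of care on the same areas is allowed after the Week 16 visit only if it contains no prohibited medication. "If those standard of care treatments include prohibited medications, the subject should be discontinued from the study".
- **IGA area (10.3.1.1).** The IGA is scored "excluding the following areas: knees, elbows, neck, palms, soles, axillae, groin, and scalp". The face is not on that list, but Sections 7.1, 9.8 and 10.2.1.2 say that Baseline IGA is taken on the rest of the body, after naming face, scalp, hands and feet as areas where usual care may continue.
- **Endpoints (13.1.4.1).** The Palm/Sole Assessment is a secondary endpoint, and so is "The difference in proportion of subjects with presence of fissures on palm/soles" at Day 90.

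**The concern.** Sites have to act on Section 9.8 in real time. A double-blind subject whose palms crack after Week 4 and who goes back to a urea cream is within the rules under 9.8.1 and is using a prohibited therapy under 9.8.2. Two sites could treat identical subjects differently: one approves and records the use, the other consults on stopping study treatment. Retention and per-protocol membership would then vary for reasons unrelated to the drug.

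The second consequence is for the endpoints. The use is post-randomisation, is prompted by worsening, and is applied to the very skin on which thickening, roughness and fissures are scored. If the drug works there, more use would be expected on vehicle, which would improve vehicle scores and shrink the observed difference.

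**Working it through.** No figure in the protocol needs reproducing here. The check sets the passages side by side, followed by an illustration on assumed rates.

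**1. The agents.**

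| Place | Period | Status of urea and hydroxy acids | Limits stated |
|---|---|---|---|
| 9.8.1, first paragraph | Double-blind | May be used | Face, palms/soles; after Week 4 assessment; on worsening; investigator approval |
| 9.8.2 and Table 9-1 | During the study | Prohibited | None by area or time; Table 9-1 excepts keratolytic shampoo only |
| 9.8.1, second paragraph | Open-label extension | Prohibited content means discontinuation | Face, palms/soles; after Week 16 visit |

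The first two rows cover the same agents, skin and period with opposite answers. These sections do write exceptions out when they are meant (keratolytic shampoo; benzoyl peroxide on nontreatment days). None refers to 9.8.1.

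**2. The trigger.** Use requires IGA worsening in the face or palms/soles. Palms and soles are outside the IGA, so the condition can never be scored there. For the face it is unclear, because 10.3.1.1 does not exclude it while 9.8 takes Baseline IGA on the rest of the body. In addition, 10.3.1.1 describes a single full-body score, not one per area.

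**3. Which scores are exposed.** Table 2-1 equates Day 30 with Week 4, and use is allowed only after that assessment. Day 14 and Day 30 scores therefore precede any permitted use. Day 60 and Day 90 can be affected.

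**4. Deviation status.** Section 13.1.1 requires no significant protocol deviations for the per-protocol set. Section 13.1.2.2 says that tapering and drug holidays are not deviations, and says nothing about standard of care allowed by 9.8.1.

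**5. Illustration for fissures (all rates assumed, none from the protocol).** Let presence at Day 90 without such use be 60% on vehicle and 40% on active, a 20-point difference. Let w be the share of an arm that worsens and qualifies, and k = uptake × clearance, varied from 0.25 to 0.75. Observed rate = unaided rate − w × k.

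- w = 20% vehicle, 10% active: k = 0.25 gives 0.550 − 0.375 = 17.5 points; k = 0.75 gives 0.450 − 0.325 = 12.5 points.
- w = 30% and 10%: k = 0.25 gives 0.525 − 0.375 = 15 points; k = 0.75 gives 0.375 − 0.325 = 5 points.
- w = 30% in both: both rates fall and the difference stays at 20 points.
- w = 10% and 30% (more use on active), k = 0.50: 0.55 − 0.25 = 30 points, so the distortion reverses.

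If use is instead a share u of subjects with fissures and clearance is c, observed rate = unaided rate × (1 − u × c). With u = 30% and 10%, c = 0.3 gives 0.546 − 0.388 = 15.8 points and c = 0.5 gives 0.51 − 0.38 = 13 points. Under this form equal use of 30% with c = 0.5 still gives 0.51 − 0.34 = 17 points.

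**6. Illustration for the palm/sole score (assumed).** Take a true 0.5-grade benefit, use in 30% against 10%, and an effect g of 0.5 to 1.0 grade. At a single visit after use starts: 0.5 − g × 0.2 = 0.40 to 0.30. Averaged equally over Days 14, 30, 60 and 90, with only the last two affected: 0.5 − g × 0.2 × 2/4 = 0.45 to 0.40.

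**The case against.** **The specific governs the general.** Section 9.8.1 can be read as a narrow exception limited by area, timing, worsening and approval. The amendment summary supports that intent: its rationale is to let worsening subjects return to standard of care after Day 30, and the open-label limit is there to avoid combination treatment. On this reading only a cross-reference is missing from 9.8.2, and ineligibility there is discretionary in any case. The intent is plausible, but it does not cure the operative text, which has no exception, and it leaves the palm/sole trigger unscorable.

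**A permitted, prohibited and disqualifying act at once?** A reader might infer this from the discontinuation sentence. The documents do not support it: that sentence belongs to the open-label extension. In the Double-blind Period the conflict is between permission and prohibition with possible loss of continued treatment.

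**Contamination of the primary endpoint?** A reader might infer that facial use enters the primary IGA because the face is not excluded. The statement that Baseline IGA covers the rest of the body points the other way, and whether the face is scored at Day 90 is not settled. Palm/sole use does not reach the IGA at all.

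**Analysis belongs to the SAP.** This stands. Section 13 does not state how scores after such use are handled; it defers detail to the SAP. Analysing scores as observed is a legitimate choice, so the protocol's silence is no defect in itself. Per-protocol membership is also fixed before database lock, which limits the harm there, although the people deciding would still face two contradictory rules.

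**Conclusion.** The contradiction between 9.8.1 and 9.8.2 with Table 9-1 is direct, and the trigger cannot be applied to palms and soles as the IGA is defined. Both are faults in the protocol's conduct rules, which a SAP cannot repair. They affect treatment continuation and deviation status for double-blind subjects who worsen after the Week 4 assessment. Only that subset is affected; the documents do not say how large it is.

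The effect on endpoints is a qualified concern. It is confined to Day 60 and Day 90 scores for palms/soles and fissures, which are secondary endpoints. Dilution is the plausible direction if use is more frequent on vehicle, but neither direction nor size follows from the documents. The illustrative results, from 20 points down to 5 and up to 30 if use were more frequent on active, show only how strongly the answer depends on use by arm. They should not be quoted as an estimate of bias.

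All of this rests on the Amendment 2 wording of Section 9. A later Section 9, not shown, may already have reconciled it.

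**What to change.** 1. Reconcile 9.8.1, 9.8.2, Table 9-1 and the IGA area definition in 10.3.1.1 so that one rule and one scorable trigger govern the Double-blind Period. Which rule is the sponsor's clinical decision. State explicitly whether the face is part of the IGA at Baseline and afterwards.
2. In 13.1.2.2, beside the sentence on tapering and drug holidays, state whether use allowed by the reconciled rule counts as a protocol deviation for the per-protocol set.
3. Make sure the eCRF record that 9.8.1 already requires includes start date and body area; the protocol does not say that it does.
4. Tabulate use by arm and area.
5. Add a sensitivity analysis of the palm/sole and fissure endpoints that accounts for such use, for example with users counted as having fissures at Day 90 and palm/sole scores after the start of use set aside. Leave the main estimand to the SAP.

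The cost is a short protocol clarification, possibly two eCRF fields, one table and one sensitivity analysis. No new patients or visits are needed.

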9.8.2 Prohibited Therapies

The medications listed in [Table 9-1](#) are prohibited during the study. Balneotherapy is also prohibited during the Screening Period and during the study.

Subjects may not use concomitant keratolytics such as urea, salicylic acid, alpha, or beta hydroxyacids. Subjects may not use topical or systemic retinoids. Subjects may not take more than 3500 IU/day Vitamin A (e.g., as in a multivitamin). Use of benzoyl peroxide is permitted on nontreatment days for subjects with concomitant acne only); it must not be applied on treatment days due to risk of inactivation of trifarotene by benzoyl peroxide.

Subjects receiving excluded therapies will be ineligible for study enrollment or for continued treatment in the study, at the investigator's discretion with consultation with Mayne Pharma LLC and the medical monitor. For enrolled subjects who require prescription of a systemic azole, the principal investigator should discuss with the medical monitor whether the subject may continue in the study.

9.8.3 Restrictions

Subjects should not shower, bathe, or swim for at least 4 hours after study drug application. No occlusive dressings should be applied to areas where study drug was applied.

Subjects should only use investigator-approved emollients, and should not use them on treatment days within at least 4 hours before and after study drug application.

In addition, subjects should take protective measures to avoid exposure of treated areas to sunlight, such as applying sunscreen (except within 4 hours before and/or 4 hours after study drug application), and/or wearing protective clothing (e.g., long sleeves, hats, and covering legs and feet), and/or seeking shade or shelter from the sun.

9.9. Treatment after End of Study

After the end of the study, each subject will be treated according to standard clinical practice.

9.10. Dispensing and Storage

The test product supplied by Mayne Pharma LLC is to be used exclusively in the clinical study according to the instructions of this protocol. The investigator is responsible for dispensing the IP according to the dosage scheme and for ensuring proper storage of the IP.

The investigator must confirm the receipt of the IP with his or her signature. A copy of this receipt must be kept by the investigator and another copy will be stored at Premier Research. Until the IP is dispensed to the subjects, it must be stored at 20–25°C (68–77°F), with excursions permitted to 15–30°C (59–86°F); do not freeze and with the tube kept tightly closed in a securely locked area that is not generally accessible.

The key to the storage area is to be kept by the investigator or designee responsible for the IP. The store will be accessible only to those persons authorized by the investigator to dispense the IP.

9.11. Drug Accountability

The investigator must maintain adequate records showing the receipt, dispensing, return, or other disposition of the IPs, including the date, quantity, batch or code number, and identification of subjects (subject number) who received the IP. The investigator will not supply the IP to any person except those named as subinvestigators on the Form Food and Drug Administration (FDA) 1572, designated study personnel, and subjects in this study. The investigator will not dispense the IP from any study sites other than those listed on the Form FDA 1572. Investigational product(s) may not be relabeled or reassigned for use by other subjects. If any of the IP is not dispensed, is lost, stolen, spilled, unusable, or is received in a damaged container, this information must be documented and reported to the sponsor and appropriate regulatory agencies, as required.

Each subject will be given enough tubes of study drug to apply up to 1 tube-full (approximately 36 g of clinical trial material) per treatment day until the next study visit. Tubes will be packed 2 to a carton, and each subject will receive enough cartons to have the maximum number of tubes needed until the next study visit. The number of study drug tubes the subject needs to provide enough IP until the next visit is shown in [Table 9-2](#).

Table 9-2: Amount of Study Drug Needed Per Visit

Treatment Period	Number of Cartons	Number of Tubes
Double-blind Treatment Period		
Baseline	3	6
Day 14	4	8
Day 30	6	12
Day 60	6	12
OLE		
Day 90	3	6
Day 104	4	8
Day 120	6	12
Day 150	6	12

Each carton will be weighed before dispensing and subjects are to bring all cartons and tubes back at each study visit, whereupon study staff will weigh them again to estimate study drug use and compliance.

Upon completion of the study, the IP (partly used, unused, and empty tubes) must be left in the original packaging and returned to the sponsor or designee for destruction.

9.12. Labeling and Packaging

Labeling and packaging of IP will be performed by Catalent Pharma Solutions, Philadelphia, PA, USA.

Tubes will be packaged in cartons comprising 2 tubes each. Tubes will be labeled with inner and outer booklet labels, and carton number. Each carton will also be labeled with inner and outer booklet labels and numbered.

9.12.1 Labeling

The tubes will have a label affixed that meets the applicable regulatory requirements and may include, but is not limited to, the following: subject identifier, IP name, lot number, protocol number, carton number, caution statement, storage, and sponsor identification.

Save all empty packaging or packaging containing unused tubes for final disposition by the sponsor or contract pharmacy.

Final labeling will comply with the regulatory requirements of each country where the study will be conducted.

9.12.2 Packaging

Investigational products will be packaged in high-density polyethylene, 35×100 mm tubes weighing 50 g from which a maximum of 36 g of IP can be extracted. Trifarotene cream HE1 and vehicle will be packaged so as to be blinded to the investigator, the study clinic personnel, and the subjects.

10. STUDY PROCEDURES

Subjects must provide written informed consent before any study-related procedures are initiated, including the cessation of prohibited concomitant therapy.

Subjects who agree to participate in the photography and/or PK substudies must provide written informed consent before photographs or serial blood samples are collected.

For the timing of assessments and procedures throughout the study, refer to the Schedule of Events (Section 2.2). Throughout the study, every reasonable effort should be made by study personnel to follow the timing of assessments and procedures in the Schedule of Events for each subject. If a subject misses a study visit for any reason, the visit should be rescheduled as soon as possible.

10.1. Study Duration

10.1.1 Overall Study Schedule

The overall study duration is expected to be approximately 19 months.

The planned sequence and maximum duration of the study periods will be as follows:

1. Screening: up to 35 days (after signing informed consent, if necessary, washout may be up to 3 months, and subjects should return to the site after washout to complete the study eligibility requirements).
2. Double-blind treatment: Twice weekly for 12 weeks.
3. Optional Open-label Extension treatment: Twice weekly for 12 weeks.
4. Follow-up: 14 days after last study drug application.

The maximum treatment duration for each subject is approximately 12 weeks for subjects who choose not to continue into the OLE, and 24 weeks for those who choose to continue.

The maximum study duration for each subject is approximately 229 days (33 weeks).

10.2. Study Periods and Visits

It is suggested that quality of life assessments be conducted first to avoid any bias, and that the IGA be recorded as the first LI assessment at every visit.

10.2.1 Screening and Washout

10.2.1.1 Screening Visit (Visit 1)

The subject must complete eligibility screening within 35 days before randomization in the study. The following procedures will be performed during Screening:

1. Obtain written informed consent.
2. Assign a screening number when a subject begins screening.
3. Assess inclusion/exclusion criteria.
4. Collect demographic information.

5. Record medical history, including current therapies (e.g., prescription and nonprescription medications).
6. Perform a physical examination.
7. Measure vital signs (systolic blood pressure [SBP], diastolic blood pressure [DBP], and pulse).
8. Measure height, weight, and calculate body mass index (BMI).
9. Record IGA.
10. Record VIIS.
11. Record roughness assessment.
12. Record palm/sole assessment.
13. Record palm/sole assessment of fissuring.
14. Record ectropion score.
15. Perform a 12-lead ECG.
16. Collect blood and urine for laboratory tests.
17. Perform serum pregnancy test for WOCBP.

Procedures for rescreening subjects who initially fail to meet study entry criteria are described in Section [14.3](#).

10.2.1.2 Washout

Upon signing informed consent and entering the Screening Period, subjects will stop using physical and medical treatments for LI, including balneotherapy, and may begin to washout the prohibited topical and systemic treatments with designated washout periods, as applicable ([Table 9-1](#)). Washout may be up to 3 months, as necessary.

During washout, subjects may continue taking usual care of visible skin (face and scalp) for cosmetic reasons and of extremities (hands and feet) to avoid functional consequences on walking or moving their fingers. Subjects may shower but not bathe or swim. The IGA will be evaluated on the rest of the body at Baseline.

After completing any necessary washout of prohibited medications, subjects will return to the site to complete the study eligibility requirements ([Section 10.2.1.1](#)).

